Mathematical model- We will parameterize a model with cost data from our microcosting activities and viral suppression data from Opt4Kids and project HIV infections, HIV-related deaths, and DALYs associated with various POC VL testing interventions. We will use EMOD-HIV, an open-source agent-based transmission model to project the cost and clinical impact of implementing POC VL testing alone and as part of a CIS in Western Kenya. EMOD includes geographic patterns of (1) age-specific demographics (fertility, mortality, migration); (2) vertical transmission, (3) a detailed, user-configurable care continuum for HIV treatment and prevention interventions that can be configured to reflect differences in treatment access and health seeking behavior among children and adolescents, including heterogeneities in access and retention in care (e.g., age and sex differences in diagnosis and linkage), and (4) a detailed within-host model of HIV progression and treatment to simulate the health and transmission effects of pediatric ART (Figure 6).

Queuing model design: Operational research models are meant to simulate the behavior of a system and use data to inform decision-making. We will use *queuing models*, a specific kind of model commonly used in industrial engineering to model waiting lines or “queues”. Queuing models represent queuing systems (i.e., waiting lines) using mathematical formulas to describe the system performance, such as average waiting time and expected queue length in the system. A queuing model has the following components; an input source generating the customer arrival process, the queue capacity, the queue discipline (e.g., first-come-first-served) and the service mechanism (e.g., number of servers, service time distribution). The queuing model example input and output parameters are delineated in Table 4, which will be collected from a representative sample of 12 clinics; we will include 5 health facilities where Opt4Kids is taking place and at 7 additional facilities selected to reflect a range of pediatric patient volumes, facility sizes, and distances to the central laboratory. To further model the parameters for a wider range of facilities in Kenya, In conjunction with our colleagues at the Kenyan Ministry of Health, we

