We will use logistic regression models to identify risk factors associated with major and any DRMs. Potential risk factors of interest include individual-level (age, sex, duration on ART, prior antiretroviral exposure, prior viral suppression patterns, WHO clinical stage), clinical parameters (such as weight- or height-for-age), immunological status, family-level, HIV status of caregivers, socioeconomic status, and facility-level factors, such as volume of patients and urban/rural location. Covariates with p<0.20 in univariate analyses will be included in the multivariate models. We will also consider including interaction terms for any suspected effect modifiers such as age group of the child. The above analytic approaches will be taken for analyzing data from the NGS genotyping and phenotyping; in addition to descriptively generating the

patterns and distribution of NGS-detected DRM, including for minority variants and for mutations relevant to DTG, we will also compare them to the results obtained via CS when concurrent results are available.

To evaluate **Aim 2b**, CS and OLA simple-based DRM testing (Aim 4): To evaluate the test performance of OLA Simple (Aim 4a), we will compare test results for each codon from the OLA Simple test against a composite “gold standard” constructed from CS and Illumina sequencing (the latter performed on samples that are negative for DRMs by CS), stratified by retro- or prospective testing. We will calculate sensitivity, specificity, and positive and negative predictive values for the detection of DRMs per codon, organized by drug classes, for the OLA Simple. The above are the fundamental metrics the WHO, for example, considers in its prequalification application for in-vitro diagnostic and laboratory technologies approvals, achieving sensitivity and specificity >90% would demonstrate high test performance.

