While not our primary outcome, interim descriptive statistics of VLs over time are provided for VS at baseline and quarterly thereafter. For participants in the POC group, POC test results are used. For participants in the SOC group, SOC test results are used. Testing over time is shown descriptively using testing intervals defined by days since enrollment: Enrollment = 0-2 years prior to enrollment; 3 months = 1 day to 3 months + 6 weeks after enrollment; 6 months = 6 months +/- 6 weeks; 9 months = 9 months +/- 6 weeks. This could differ from study visits as assigned by visit staff, for example if a 6 visit was attended over 6 weeks late it could fall in the 9-month interval. If more than one test had been performed in an interval, the test closest to the target date is used.

Study Aim 1. Effect of the intervention:

All analyses of the effect of the intervention are ITT, using randomized group assignment as the exposure variable as described in the Exposure Variables section (p3).

Aim 1a: We hypothesize that the proportion with VS one year after enrollment will be higher among children randomized to POC VL testing compared to those in the control group. Our primary analysis will compare the proportion of children with VS 12 months after enrollment as defined by our primary outcome in the intervention vs. control groups, estimating the RR for the intervention effect using a modified Poisson regression model with robust standard errors, adjusting for facility and age group strata (1-9 or 10-14 years). We provide supporting descriptive statistics of the primary outcome by randomized group. Sensitivity analyses using lower cutoffs for VS follow the same methods as the primary analysis except outcomes are as specified for sensitivity analyses of the primary outcome; they present an *a priori* sensitivity analysis comparing VS at 12 months defined as <40 copies/mL. A *post hoc* sensitivity analysis defines VS at 12 months as <400 copies/mL.

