Additional analyses including multivariate modified Poisson regression models will estimate associations between VS and all potentially related individual-level factors (such as age, sex, duration on ART, prior VS patterns (e.g., previously virally suppressed vs. not), and

family demographics), as well as facility factors (such as patient volume, staff volume, urban/rural location, and tier of facility), in order to explore predictors of VS in this context. We will also do a secondary analysis separating the outlined outcomes for children on 1st vs. 2nd line therapy.

Validation of POC HIV-1 VL tests

We intend to validate POC HIV-1 VL testing against current in-country gold standard VL testing by generating concordance/discordance rates and Cohen's kappa to determine assay agreement for VS using <1000 copies/mL. We will also conduct sensitivity analyses to determine concordance rates using lower thresholds of VL cut offs for VS (down to <40 copies/mL, the lower limit of quantification for the POC VL testing).

Study Aim 2 (DRM testing)

We hypothesize that we will find high levels of antiretroviral DRMs in this population, and both individual factors, such as prior exposure to antiretrovirals, and facility-level factors, such as facility type, will predict the presence of DRMs. We will describe the proportion of episodes of viremia (VL \geq 1000 copies/mL) that were tested for DRMs by randomization group. Among those tests, we will also describe the proportion of samples that have any DRMs by HIV drug classes, e.g. NRTIs, NNRTIs, and PIs. We will report the proportion of samples with each type of mutation detected by drug class, and further group these mutations into major and minor ones. For example, we will examine major mutations in M184V/I and K65R for NRTIs, K103N, Y181C, G190A, and V106M for NNRTIs, and V82A, I76V, 184V, L47A, L90M, M46I, and D30N for PIs. We will report the frequency of drug regimen changes being recommended as a result of the DRM testing result, and, among those recommended to change, the proportion who actually do change prior to the month 12 visit.

We will use multivariate logistic regression models to identify risk factors associated with major and any DRMs. We will also explore how sociodemographic, behavioral, clinical, and facility factors may be contributing to the DRM patterns we observe.

ART regimens over time

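### Facility-level predictors of suppression and drug resistance are tested in child-level models with no allowance for clustering, although the trial appears to run at only five facilities

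*SAP*

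**What the plan says.** **Suppression.** Under Other associations with VS, the SAP states: "Additional analyses including multivariate modified Poisson regression models will estimate associations between VS and all potentially related individual-level factors". The same sentence adds "facility factors (such as patient volume, staff volume, urban/rural location, and tier of facility"). The stated purpose is exploratory.

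**Drug resistance.** Under Study Aim 2 (DRM testing), the SAP hypothesises that "facility-level factors, such as facility type, will predict the presence of DRMs". It continues: "We will use multivariate logistic regression models to identify risk factors associated with major and any DRMs". The protocol's Data Analysis Plan for Aim 2 lists "facility-level factors, such as volume of patients and urban/rural location" among the candidate risk factors and adds an entry rule: "Covariates with p<0.20 in univariate analyses will be included in the multivariate models".

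**Variance.** Neither document names a random effect, GEE, cluster-robust variance or facility-level analysis for these models. Robust standard errors appear only in the primary Aim 1a model, "using a modified Poisson regression model with robust standard errors, adjusting for facility and age group strata", and no cluster level is given there.

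**Number of facilities.** The SAP gives none. The only figure is in the protocol under Aim 3b: Modeling, in the queuing-model text: "we will include 5 health facilities where Opt4Kids is taking place".

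**The concern.** Patient volume, staff volume, location and tier take one value per facility. With five facilities, the evidence on any of them is five data points, however many children are measured. A child-level regression treats each child as separate evidence, so ordinary differences between clinics that have nothing to do with the modelled factor can appear as a precise effect of that factor. Several such factors in one model can also use up all the between-facility information.

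At stake are the confidence intervals and p-values for facility factors, including a stated Aim 2 hypothesis.

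**Working it through.** **Inputs**
- Facilities: 5 (Protocol, Aim 3b).
- Children with a 12-month outcome: 700 × 0.9 × 0.9 = 567 (SAP, Power calculations). Per facility, if spread evenly: 567/5 = 113.4.
- Children with a DRM test: 284 × 0.35 ≈ 100 (same section). Per facility: 100/5 = 20.
- Significance level: 0.05 (SAP, General statistical considerations).
- Assumed, because the documents give no value: the ICC, an even spread over facilities, one binary factor splitting facilities 2 against 3, and 70% suppression. DRM prevalence is taken as 80% (the SAP's own example) and 90% (the national survey in the protocol's Preliminary Studies found 89% with any mutation).

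**The plan's own figure.** The documents give no power, standard error or ICC for facility predictors. The nearest figure is power 0.80 for 65% vs 76% with 284 per arm. Exact enumeration of Fisher's test gives 0.7987, so the sample size used here is the plan's.

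**Degrees of freedom between facilities**
- One factor: 5 − 2 = 3. The critical t is 3.18, against 1.96 for the normal.
- Two DRM factors: 5 − 1 − 2 = 2.
- Four suppression factors at 1 df each: 5 − 1 − 4 = 0. A three-level tier gives 6 columns of rank 5, which cannot be estimated.
- Four factors plus the four indicators needed for five facilities: 9 columns of rank 5, so the facility factors cannot be identified.

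**Size of the error.** The design effect is 1 + (m − 1) × ICC, and the child-level standard error is too small by its square root. For suppression at ICC 0.01, 1 + 112.4 × 0.01 = 2.12, and √2.12 = 1.46. Rejection rates come from beta-binomial simulation (40,000 runs, no true factor effect), with a robust modified Poisson model for suppression and a logistic model for DRMs.

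| ICC (assumed) | Suppression: design effect | SE too small by | Rejection at nominal 5% |
|---|---|---|---|
| 0 | 1.00 | 1.00 | 5% |
| 0.005 | 1.56 | 1.25 | 12% |
| 0.01 | 2.12 | 1.46 | 18% |
| 0.02 | 3.25 | 1.80 | 28% |
| 0.05 | 6.62 | 2.57 | 45% |

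| ICC (assumed) | DRM: design effect | Rejection, 80% prevalence | Rejection, 90% prevalence |
|---|---|---|---|
| 0.01 | 1.19 | 7% | 3% |
| 0.02 | 1.38 | 9% | 4% |
| 0.05 | 1.95 | 15% | 8% |

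At 90% prevalence the logistic Wald test is conservative in samples this small, which offsets much of the inflation. At 80% prevalence the protocol's p<0.20 screen admits a null facility factor in 25%, 28% and 37% of runs at these three ICCs.

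**Four suppression factors together** (600 runs, illustrative facility values). Each is falsely significant in about 17–19% of runs at ICC 0.01 and 46–52% at ICC 0.05. At least one is in 44% and 85%, against 14% at ICC 0.

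**Alternatives.** A t test on the five facility means (3 df) rejects in 4.9–5.4% of runs at every ICC from 0 to 0.10, for both outcomes. Cluster-robust standard errors with a normal reference reject in about 20%. In the four-factor model they collapse to about 10⁻¹¹.

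**If there were more facilities.** With ten (an assumption), m = 56.7 and the design effect at ICC 0.02 is 1 + 55.7 × 0.02 = 2.11. That is practically the five-facility value at ICC 0.01, so rejection would be about 18%.

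**The case against.** Several points on the other side stand.

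- **The error is conditional.** A reader might infer that the standard errors are wrong in every case. The documents give no ICC; at ICC 0 the child-level test is correct, and adjustment for child-level covariates may lower the residual ICC. The simulations are unadjusted and assume equal facility sizes.
- **Five is not certain.** It comes from one queuing-model sentence that does not say these are all the sites, and the protocol's study methods foresee further sites sending samples to a hub. Five is the natural reading, but the exact degrees of freedom depend on it.
- **Saturation is limited to suppression.** A reader might infer that it covers both outcomes. For DRMs the SAP gives one example of a facility factor and the protocol two. Even for suppression the list is only illustrative, so saturation needs all four factors entered together.
- **Aliasing with facility is not established.** The SAP's predictor model does not say that facility indicators are included; they appear in its primary model and in the protocol's predictor model. Were both fitted, the factors could not be estimated at all, which is a different failure from false significance.
- **Use in scale-up is not shown.** A reader might infer that these predictors will steer it. The protocol says that only of the study's findings in general, and machine placement comes from the queuing model.

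The exploratory purpose does not settle the matter. It describes the suppression models, but the SAP states facility-level prediction of DRMs as a hypothesis, and an exploratory interval still needs a valid width. Nor is it safe to assume a zero ICC: the plan stratifies randomisation by facility and adjusts for it, and for suppression an ICC of 0.005 already more than doubles the error rate.

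**Conclusion.** The point holds in conditional form. If facilities differ beyond the modelled factor, following the SAP gives standard errors for facility factors on suppression that are too small by about 1.25 to 2.6 times over ICC 0.005 to 0.05. With all four suppression factors in the model, there is no between-facility information from which to form a valid standard error. For DRMs the problem is the same in kind but modest, and at 90% prevalence rejection stays below 5% until the ICC exceeds 0.02. The results rest on five facilities of equal size, a 2-against-3 split and assumed ICCs.

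A reader might infer that the trial's main result is in doubt. It is not: children are randomised within facility and the primary model adjusts for facility. This is a correction to secondary analyses that should be made, and it does not threaten the primary conclusion.

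**What to change.** Change the SAP wording under Other associations with VS and Study Aim 2:

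1. State the number of study facilities.
2. In the child-level predictor models for suppression and DRMs, fit facility as a fixed effect and remove the facility-level factors.
3. Tabulate suppression and DRM prevalence by facility beside each facility's volume, staffing, location and tier, without p-values.
4. Treat the Aim 2 facility hypothesis as descriptive.
5. If a test is kept, use one facility factor on facility-level summaries (3 df with five facilities), and label it exploratory and low-powered.

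Limiting the model to one facility factor and labelling it exploratory would remove the saturation, but the test would still need to be made at facility level. Cluster-robust standard errors should not be substituted, since with five clusters they reject in about 20%.

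No data collection changes. What is lost is a set of p-values for facility factors that the design cannot support.

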## B. Hypotheses

We hypothesize that 1) viral suppression rates will be higher among children with access to POC VL testing; 2) time to suppression will be shorter compared to children with standard VL testing; 3) we will detect >90% concordance for categorization of plasma VL as <1000 or =>1000 copies/mL for POC (via GeneXpert) vs. gold standard (via Abbott) VL testing; 4) hypothesize that targeted DRM testing will shorten time to viral suppression; 5) pediatric POC VL testing and DRM can be implemented in HIV care clinics in Kenya at reasonable costs and is cost-effective compared to standard-of-care adherence monitoring; and 6) modeling tools to inform placement of POC VL machines in a geographic area will be usable to policymakers.

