## D. Preliminary Studies/Progress Report

**Pediatric viral suppression at FACES:** Drs. [name], multiple-PI on this proposal, [name], co-investigator, and colleagues have assessed prevalence of treatment failure amongst children undergoing routine VL testing at FACES sites between June 2014–May 2015. Among 1190 children and young adolescents 0-14 years of age undergoing routine VL testing, 748 (63%) were virologically suppressed. In multivariable analysis, unsuppressed children were more likely to be male (adjusted odds ratio (aOR) 2.1, 95% Confidence Interval (CI) 2.1-3.6) and have had an ART regimen change (aOR 2.0, CI 1.0-3.7) than suppressed children. A third of children with virologic failure never had a follow-up viral load. Among those that did, VL suppression was only achieved by 23% versus 93% among those suppressed at baseline ( $p<0.0001$ ). Mean time for a follow-up VL in children with virologic failure was 11.3 months (95% CI 9.5-13.2).

[figure not shown]
Table 2. Patterns of HIV DRMs among children and adolescents in Kenya, 2013	
Specific mutations with VL <math>\geq</math> 1000 copies/mL	N (%) (n=136)
NRTI, any	108 (79%)
M184V	103 (75%)
K65R	6 (4%)
1 TAM	13 (10%)
2 TAMs	7 (5%)
3 TAMs	15 (11%)
L74V	36 (27%)
NNRTI, any	117 (86%)
K103N	46 (34%)
Y181C	43 (32%)
G190A/C	39 (29%)
PIs, any	0
Any mutations	121 (89%)

**National drug resistance surveillance for children in Kenya:** In 2013, [name], site-PI on this proposal, led the National AIDS and STI Control Programme's (NASCOP) cross-sectional, nationally-representative survey of acquired HIV DRMs among adults and children on ART for at least 12 months in Kenya. Virologic failure was defined as a VL  $\geq$ 1000 copies/mL per national guidelines and 90% of the children were on a NNRTI-containing regimen. Overall, 31% of the 461 children had virologic failure, as compared to only 11% of the adults. Of the children with virologic failure, 89% had at least one DRM detected. Seventy-nine percent had DRMs to NRTIs, 86% to NNRTIs, 77% to both NRTIs and NNRTIs, and 0% to PIs (though PI use was infrequent in this cohort). The most common DRMs were M184V and L74V for NRTIs and K103N, Y181C, and G190A for NNRTIs (Table 2). In addition to conducting this survey, [name] was involved in training and capacity building of providers in handling DRM testing results and results dissemination.

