For those assigned to the control arm, VL testing will be conducted per national guidelines (as outlined above) through laboratory networking and transport to a centralized laboratory as the SOC. Children in the SOC arm who are newly initiating ART will have blood collected prior to ART initiation for future VL and DRM testing to be conducted at completion of study follow up. These results will be returned to clinical providers and patients/caregivers after the study. Additionally, in order to have comparable outcomes, POC VL will be conducted on ALL SOC participants at 12 and 24 months of follow up. Study nurses will prompt providers to order follow-up VL tests for those who qualify to ensure uptake of VL testing in both study arms.

We will batch test all stored samples for gold standard VL testing towards the end of the study period for both the arms (n= up to 700 samples), and generate concordance/discordance rates and Cohen's kappa to determine assay agreement. We will also conduct sensitivity analyses to the concordance rates at lower thresholds of viral load cut offs for viral suppression (down to <40 copies/mL, the lower limit of quantification for the POC VL testing). To conduct the in-country

gold standard HIV-1 VL testing (or quantification), we will build on our existing partnership with the KEMRI-CDC HIV Research Laboratory, led by [name], a collaborator on this proposal. The KEMRI-CDC facilities are located immediately outside of Kisumu. The KEMRI-CDC HIV Research laboratory utilizes state of the art HIV-1 quantification technologies by using Abbot m2000sp/RT, Roche CAP/CTM, and Roche C8800 systems (cite). Overall, the two main assay platforms, the Abbot vs. the Roche platforms, both perform extremely well, with subtle difference in accuracy and precision of each platform (cite). As we get closer to the time of running our samples for this validation, we will determine which specific platform to use depending on logistical aspects, such as current usage of the platforms. These platforms can run the assays with 0.5-1mL of plasma, which will already be stored in cryovials of this volume at the same facility. For each sample analyzed, we will receive printed reports noting exact quantification or below or above the limits of quantification.

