For our secondary analysis, we will compare the proportion with viral suppression at 24 months after enrollment and follow the analytical plan detailed above for the primary outcome. We will also compare time to viral suppression using a Cox regression model limited to individuals who were not already suppressed at 1st POC VL testing or those initiating ART. The primary predictor will be intervention vs. control arm, with stratified baseline hazards by site, adjusting for other predictors that could confound this relationship, such as the ones listed above. As noted above, although the VL testing schedule is generally different in intervention vs. control arms, the frequency of VL assessment is not different among those on ART but not suppressed; in both intervention and control arms, children without viral suppression at their first VL test while in the study are subsequently tested every 3 months until achieving suppression. The exception is for children newly initiating ART at study enrollment, the first VL test is at 6 months in the control arm and 3 months in the intervention arm; to align the outcome assessment in those newly initiating ART, we will exclude from the analysis the initial 3-month viral load in the intervention arm for those participants. In a sensitivity analysis, we will exclude those newly initiating ART altogether (estimated to be 24 individuals).

For **Aim 1b**, the quantified values will be transformed on a log scale. Then we will correlate log copies when detected, <40 copies/mL but detected, or not detected. We will use Cohen's kappa statistic, generating 95% confidence intervals, to determine the agreement in concordance and discordance of the POC VL testing against the gold-standard testing. We expect that as the quantity of viral copies/mL detected increases, so will the concordance rates between the two platforms. We will also assess the agreement between the two platforms using a Bland-Altman plot. For the discordant results, we will compare descriptively the results found in each platform.

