Power for the study is based on the primary outcome of proportion of VS in children in the intervention vs. control arms at 12 months after enrollment for each child (Aim 1). We estimated requiring a sample size of 90% (630) of an estimated 700 children eligible to enroll to have 80% power to detect an effect size of a difference between arms of at least 11%. Accounting for 10% loss to follow-up over 12 months, this sample size is expected to provide total of 567 children (or 284 per arm) with outcomes for analysis. These calculations are based on Fisher's exact test, two-sided $\alpha=0.05$, and initial VS rates of approximately 65% (estimated from historical facility data).

Table 5: Effect sizes and power calculations				
VS rates, control (SOC) vs. intervention (POC) arms	Difference (effect size)	Power	Expected Total N for analysis	Expected N per arm for analysis
65% vs. 70%	5.0%	0.22	567	284
65% vs. 72.5%	7.5%	0.45	567	284
65% vs. 75%	10%	0.71	567	284
65% vs. 76%	11%	0.80	567	284
65% vs. 77.5%	12.5%	0.89	567	284
65% vs. 80%	15%	0.98	567	284
70% vs. 80%	10%	0.76	567	284
70% vs. 82.5%	12.5%	0.93	567	284
70% vs. 85%	15%	0.99	567	284

A power calculation was also performed for how precisely the prevalence of DRMs could be estimated. With 284 participants randomized to the intervention arm, we expected approx. 35% (100) to not achieve VS at their 1st POC VL test and undergo DRM testing, and we would be able to estimate prevalence of DRMs to within +/- 5% to 10% of the 95% CIs. For example, for a class of DRMs with prevalence of 80%, we anticipate generating exact 95% CIs of 71.3%-87.0%; a less common DRM at 10% will generate 95% CIs of 5.1%-17.1%.

Outcome Variables

Aim 1 primary outcome

Our study's primary outcome is the child's VS (defined as $VL < 1000$ copies/mL) at 12 months after enrollment (defined as from a blood draw within 12 months +/- 16 weeks after the enrollment date). VL quantity is determined using results from the study's POC HIV VL GeneXpert test result which was planned for both randomization groups at the 12-month time point. Where a participant has no POC result available at 12 months but does have a standard laboratory VL available at 12 months, the standard laboratory VL is used. A month is considered to be 28 days.

Aim 1 VL sensitivity analysis outcomes

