POC group was not consistently performed quarterly due to COVID interruptions either delaying or preventing in-person visits, especially at study months 6 and 9. Also, for SOC children, the routine testing schedule did not necessarily align with study enrollment, resulting in SOC VLs performed at enrollment only for a subset of SOC children, and subsequently, SOC was not necessarily performed quarterly. Because in neither arm was time to VS measured consistently, we changed from comparing time to VS by estimating a hazard ratio from Cox regression, to comparing VS at 12 months by estimating a relative risk from a modified Poisson regression so that our outcome is measured in the same manner in both groups. Second, because in SOC only a subset were tested at enrollment, we used first VL test up to and including 6 months to identify SOC children who were initially unsuppressed. Third, we defined the cutoff for being initially unsuppressed and for achieving VS after enrollment to be based on 40 copies/mL to allow us to explore the question of value of our intervention in those not clearly initially suppressed. After unblinding, we discovered that enrollment VL data in those with both POC and SOC tests showed that POC tests missed a noticeable number of those with $VL > 40$ by SOC, but not in those with $VL > 400$ copies/mL; to reduce any bias from differences in the tests we changed our plan to use a cutoff of 400 copies/mL both for identifying initially unsuppressed children and for the VS outcome at 12 months for this analysis.

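### The POC viral load validation relies on overall concordance and kappa, so it gives no estimate of the share of viremic samples that the POC test misses

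*SAP*

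**What the plan says.** The SAP, under Validation of POC HIV-1 VL tests, plans to compare POC with the in-country gold standard by "generating concordance/discordance rates and Cohen's kappa to determine assay agreement for VS using <1000 copies/mL". It repeats concordance at lower cut-offs, down to 40 copies/mL. It sets no pass mark for either measure.

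The one figure to compare against is in the protocol, B. Hypotheses: "we will detect >90% concordance for categorization of plasma VL as <1000 or =>1000 copies/mL". It is worded as an expectation.

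The protocol's Data analysis and interpretation section (Aim 1b) plans more than the SAP: correlation on the log scale, a 95% CI for kappa, a Bland-Altman plot, and a look at disagreements: "For the discordant results, we will compare descriptively the results found in each platform". None of these has an acceptance limit. The SAP neither repeats them nor lists them among its changes.

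For the other new assay, OLA Simple, the same protocol section plans sensitivity, specificity and predictive values, and names 90% for sensitivity and specificity as the level that shows high performance.

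Under Changes to the analysis plan, the SAP records that in enrollment samples with both tests "POC tests missed a noticeable number of those with" more than 40 copies/mL by the standard test. The same sentence says this was not seen above 400 copies/mL. It gives no counts.

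**The concern.** The two errors have different consequences in this trial. A POC result of 1000 copies/mL or more leads to targeted resistance testing and adherence work in the intervention arm. A viremic child read as suppressed gets neither on the strength of that result. A false alarm leads to extra testing.

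Overall concordance adds the two errors together and divides by all samples, most of which are expected to be suppressed. Kappa corrects for chance agreement but is also blind to direction. A reader given only these two figures cannot tell how often the test misses viremia. That is the figure needed for the scale-up which the validation is meant to support. The POC result is also the first-choice measure of the primary outcome in both arms, so its direction of error matters beyond Aim 1b.

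**Working it through.** **Inputs**
- Concordance C = 90%, the edge of the protocol's hypothesis.
- Viremic share V = 35%, from the SAP power section: "initial VS rates of approximately 65% (estimated from historical facility data").
- V = 31%, from the national survey in the protocol's preliminary studies: "Overall, 31% of the 461 children had virologic failure".
- V = 24%, from the 76% suppression rate in the intervention arm in Table 5 (100% − 76%).
- Validation sample: gold-standard testing of stored samples "for both the arms (n= up to 700 samples").

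The documents do not state the viremic share of the stored samples. Using the three rates above for it is an assumption.

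**The plan's own figure.** The SAP says "we expected approx. 35% (100) to not achieve VS at their 1st POC VL test and undergo DRM testing". With 284 in the arm, 0.35 × 284 = 99.4, which agrees. As a check on the planning rates, exact two-sided Fisher power for 65% vs 76% with 284 per arm is 0.799 (stated 0.80).

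**Missed share.** If a fraction f of the discordant pairs is downward (gold standard ≥1000, POC <1000), then

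missed share = f × (1 − C) / V, and sensitivity = 1 − missed share.

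**Kappa.** With all discordance downward, the POC viremic share is V − 0.10, so

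pe = V(V − 0.10) + (1 − V)(1.10 − V), and kappa = (0.90 − pe) / (1 − pe).

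- V = 0.35: 0.10/0.35 = 28.6%; pe = 0.0875 + 0.4875 = 0.5750; kappa = 0.3250/0.4250 = 0.765.
- V = 0.31: 0.10/0.31 = 32.3%; pe = 0.0651 + 0.5451 = 0.6102; kappa = 0.2898/0.3898 = 0.743.
- V = 0.24: 0.10/0.24 = 41.7%; pe = 0.0336 + 0.6536 = 0.6872; kappa = 0.2128/0.3128 = 0.680.

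| Viremic share | Missed, all downward (kappa) | Missed, even split (kappa) |
|---|---|---|
| 35% | 28.6% (0.765) | 14.3% (0.780) |
| 31% | 32.3% (0.743) | 16.1% (0.766) |
| 24% | 41.7% (0.680) | 20.8% (0.726) |

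At 35% viremia, kappa is 0.765 when 28.6% are missed and 0.780 when 14.3% are missed. It barely separates the two.

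**In whole samples.** With 700 samples, 245 of them viremic, concordance strictly above 90% allows at most 69 discordant pairs (631/700 = 90.1%). If all are downward, 69/245 = 28.2% are missed.

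**The reverse question.** At 35% viremia and no false alarms, a sensitivity of 90% corresponds to concordance of 1 − 0.35 × 0.10 = 96.5%. Concordance of 90% therefore does not secure 90% sensitivity.

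**Precision of the alternative.** With 221 of 245 viremic samples detected (90.2%), the exact 95% CI is 85.8% to 93.6%. Near 90%, the approximate half-width is 1.96 × √(0.09/245) = 3.8 percentage points for sensitivity, against 1.96 × √(0.09/700) = 2.2 points for concordance.

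**The case against.** The case against has real weight.

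- *The protocol can show direction.* A Bland-Altman plot shows systematic bias between quantitative assays, and the discordant pairs are to be described. This stands. But average bias on the log scale is not the miss rate at 1000 copies/mL, and neither analysis gives an estimate with an interval. A reader might infer that the SAP has dropped these analyses. The documents show only that it does not repeat them.
- *The evidence nearest 1000 is reassuring.* The misses were noted above 40 copies/mL but not above 400. This stands and makes the worst case less likely. Without counts, and from enrollment pairs and not the planned batch of stored samples, it does not settle the matter. It would be wrong to read the SAP as having found one-way error at 1000.
- *There is no acceptance rule.* A reader might infer that the test would be declared valid at 90% concordance. The documents do not say so: the figure is a hypothesis, and kappa has no threshold.
- *Kappa falls as suppression rises.* True: from 0.765 to 0.680 in the table. So a claim that the whole assessment gets easier as suppression improves would be too strong. It holds for concordance alone.
- *The consequences are limited.* Children in the intervention arm are retested quarterly, so one missed result need not be the last. Both arms are assessed by POC at 12 months, so a shared error does not by itself favour an arm. The protocol also treats the assay's analytical performance as established.
- *OLA Simple makes categorical calls, while viral load is quantitative.* This is a fair reason not to carry the 90% level across. It is no reason to omit the two error rates at a cut-off that the plan itself uses to classify results.

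**Conclusion.** The point holds as a gap in the planned measures, and it is worth correcting. Concordance and kappa at 1000 copies/mL cannot show how many viremic samples the POC test misses, and no other planned analysis estimates that share.

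At 90% concordance, the missed share could be as high as about 29% at 35% viremia, 32% at 31% and 42% at 24%. These are ceilings. They assume that every discordant pair is downward, and that the stored samples have the viremic shares taken from the documents. An even split gives 14%, 16% and 21%.

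A reader might infer that 29% or more would be missed. At 35% viremia with concordance above 90%, the share must stay below 28.6%. A ceiling of 29% or more requires viremia of about 34.5% or less (0.10/0.29). The documents give no evidence that misses of this size occur.

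**What to change.** In the SAP, under Validation of POC HIV-1 VL tests, add the two-by-two table of POC against gold standard at 1000, 400 and 40 copies/mL. From each table report:
- sensitivity: at the main cut-off, the share of samples with gold-standard VL ≥1000 that POC also calls ≥1000;
- specificity: the share of samples below the cut-off by gold standard that POC also calls below it;
- an exact 95% CI for each.

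Base the validation conclusion on these. Keep concordance, kappa with its CI and the Bland-Altman plot as supporting results, and state in the SAP that the protocol's additional analyses remain planned.

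Date the addition as made after unblinding, because paired POC and standard results have already been examined. Label any numeric benchmark for sensitivity or specificity as post hoc.

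The cost is SAP wording and a tabulation of data already planned. The drawback is precision: sensitivity rests on the viremic samples only, about 245 if 35% of 700 are viremic, so its interval is wider than that for concordance. An observed 90.2% would have a CI of about 86% to 94%.
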